swallowing sounds and vibration information are equivalent [78, 79], and support our two-sensor method as superior to a single acoustic detector [79, 80]. In fact, our findings confirm that swallowing signals from both sensors provide useful information about swallowing function. Hence, our subsequent research of swallowing physiology with these sensors using concurrent VF images advanced our understanding of the sources of swallowing-related vibrations and sounds.

**Figure 6 –** Our results for Aim 2: (A) A summary of differences between swallowing sounds and vibrations among groups of study. Red/black circles indicate that the axis/mic in “Comparison couple” column has the higher value in a specific feature mentioned in “Features” column than the mic/axis. The column highlighted in light green and five rows highlighted in light orange indicate group/features with the largest number of dissimilarities. (B) A summary of directional differences. All dots (red and black) indicated the existence of directional dissimilarities. Axes column demonstrates which two axes are compared to each other. Red dots indicate that the first axis in the axes column has a higher value of the computed feature in features column than the second axis, while black dots indicate the second axis has a higher value than the first axis.

As per Aim 3, we clearly demonstrated that swallowed fluid viscosity strongly influences the swallowing assessment (Figure 7 summarizes the main results of [70]). We found that HRCA can detect several statistical differences between unsafe swallows of viscous fluid, in which clinically significant aspiration and laryngeal penetration occurred, and safe swallows that exhibited airway protection scores that fall within the normal range for healthy people [81]. This is of interest because aspiration of thicker liquids has been shown to produce higher rates of pneumonia and longer hospitalization durations than aspiration of thin liquids [82]. Past research has suggested that thickening agents used during videofluoroscopy exams exhibit non-Newtonian fluid properties, which lead to the reduced aspiration rate in dysphagic patients [83, 84].

Based on this research by our team, [name] received the **Presidential Early Career Award for Scientists and Engineers** in 2016. Overall, the project was very successful as all three aims were successfully

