**A1.c. Justification and feasibility – Preliminary studies:** In our preliminary research using an artificial intelligence method was used to differentiate swallows made by healthy subjects and the least impaired swallows produced by patients with OPD [70]. A total of 55 healthy participants (28 men, 27 women, mean age 39) with no history of swallowing disorders, head or neck trauma or major surgery, chronic smoking, or other conditions which impair swallowing performance, completed a total of 30 independent swallows of several liquid viscosities while their head was in a neutral position. The non-healthy participants consisted of a total of 53 patients (34 men, 19 women, mean age 63) with suspected dysphagia who were undergoing a VF evaluation at the discretion of the examining clinicians and based on patient needs, rather than an artificially controlled, standardized data collection procedure. Presentation order, head position, and other environmental factors were unique for each patient. The materials swallowed during the examination were of comparable consistencies (thin (<5 cps), 'nectar' (300 cps), 'honey' (2000 cps) consistency liquids) to those provided to healthy subjects based on available product information and qualitative guidelines. Using all of these swallows from both groups, we built an artificial intelligence method [70] based on deep belief networks [107], one of the newest forms of artificial neural networks [108], which combines multiple neural networks in different layers into a single decision process. Figure 9 summarizes our results. Our combined deep belief network configuration also demonstrated generally

Combination Network	Input Network	Structure			Statistical Metrics		
		Specificity	Sensitivity	Accuracy			
1-Layer	Small 1-Layer	90.7	83.7	87.2			
	Small 2-Layer	93.3	81.6	87.5			
	Small 3-Layer	90.9	82.2	86.5			
	Large 1-Layer	93.0	81.7	87.4			
	Large 2-Layer	96.9	85.7	91.3			
	Large 3-Layer	98.5	75.3	86.9			
2-Layer	Small 1-Layer	94.3	80.7	87.5			
	Small 2-Layer	92.0	83.3	87.6			
	Small 3-Layer	87.5	84.2	85.9			
	Large 1-Layer	97.5	79.7	88.6			
	Large 2-Layer	96.2	81.1	88.7			
	Large 3-Layer	97.8	77.6	87.7			
3-Layer	Small 1-Layer	91.1	83.7	87.4			
	Small 2-Layer	92.0	82.9	87.5			
	Small 3-Layer	83.3	77.4	80.3			
	Large 1-Layer	97.5	78.3	87.9			
	Large 2-Layer	95.4	78.0	86.7			
	Large 3-Layer	98.5	75.9	87.2			

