**Figure 9 – Preliminary results for Aim 1.** Using different configurations of artificial neural networks, we can achieve very high accuracies. In this case, a 1-layer combination of two large 2-layer networks for each axis provided the best results (bolded above).

greater sensitivity than our single-axis networks. But we do not have concurrent VF validation of the data obtained from the healthy people. Collection and analysis of these data will complete the range of swallow function and enable completion of our 2nd and 3rd aims, which seek to develop an HRCA impairment severity continuum.

**A1.d. Experimental approach:** STEP 1: We will collect concurrent VF and HRCA recordings from 70 healthy subjects (35 females and 35 males) with no previous history of swallowing difficulties who are age matched to our database of swallows from patients with OPD. Each subject will complete five swallows of 3mL thin liquid and five swallows of self-selected, comfortable volume of thin liquid from a cup, in a head-neutral position. STEP 2: We will first measure nine kinematic measures with VF (onset, offset, and time to peak hyolaryngeal excursion; laryngeal closure and reopening; UES closure and reopening; onset and offset of tongue base to posterior wall contact), penetration-aspiration scale scores [109], and pharyngeal retention/residue scores [89, 110, 111, 112].

STEP 3: Pre-process all HRCA recordings per steps taken in previous publications [29, 30, 71], to remove any disturbances and diminish noise in these recordings. STEP 4: VF results (STEP 2) will be equated with HRCA signal features and categorized by bolus volume of the swallowed material, these data will be combined with the data from over 4000 patient swallows from our previous R01 grant.

[figure not shown]

Figure 10 – Our proposed experimental and data analysis approach for Aim 1.

STEP 5: We will develop an algorithm based on the state-of-the-art machine learning concepts that will differentiate between healthy controls and people with suspected OPD whose swallows did not exhibit OPD (see Figure 10). Specifically, we will analyze a random 70% training subsample and use the deep belief machine learning approach as in our preliminary work [70]. Once modeling is complete, the remaining 30% validation subsample will be used to obtain accuracy estimates devoid of model overfitting.

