**A1.e. Data interpretation:** In STEP 2, [name] will train doctoral students to evaluate all VF dependent variables and establish their inter- and intra-rater reliability (intraclass correlation coefficient above 0.9 for continuous variables and kappa above 0.75 or percent exact agreement above 80% for categorical variables), in the measurement of kinematic event timing, and assignment of P-A and pharyngeal retention/residue scores. They will use ImageJ image processing software, to measure penetration-aspiration scores, and kinematic and pharyngeal retention/residue measures from all swallow recordings in this new set of healthy swallows, and complete the same measurements from the remaining 3900 swallows in our database that did not undergo the complete kinematic analysis that we performed to produce the preliminary data presented in section A2.c. To ensure their judgments do not drift over time, we will perform ongoing reliability measures using the same criteria, through a rolling re-analysis of a randomly selected 10% of analyzed swallow recordings. Then, to understand the accuracy of the developed HRCA analysis algorithm using only the training subsample in STEP 5, we will begin by calculating a confusion matrix [85]. The confusion matrix will be calculated by comparing the algorithm's output with scores from STEP 2. The confusion matrix will be then used to calculate false positives, false negatives, true positives and true negatives, and lastly sensitivity, specificity, predictive values and likelihood ratios for the algorithm. These values will be initially calculated using the leave-one-out approach, but we will then repeat the analysis with 10-fold cross-validation. Then in STEP 5, we will use the number of correctly and incorrectly HRCA-detected swallows to calculate the sensitivity and specificity values, again using the leave-one-out approach (the most exhaustive and computationally expensive cross-validation approach) and 10-fold cross-validation. We have proposed state-of-the-art machine learning methods based on deep learning as our primary analysis, but we will also consider other techniques such as classification tree methods [113], and generalized linear models due to their ability to produce simpler prediction rules for ease of use, cognizant of the potential loss of some accuracy compared to deep learning. Finally, we will use the validation subsample to obtain authoritative measures of accuracy devoid of risks of model overfitting.

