**A2.b. Justification and feasibility – Review of relevant literature:** To accomplish our goal, it is necessary to equate HRCA signals to standardized and validated measures of swallow impairment and airway protection. As discussed in A1.b, the PAS differentiates normal vs. disordered airway protection [81]. More recently, the MBSImP has become widely accepted in both clinical and research domains as the gold standard for interpreting VF data to determine the degree of swallowing impairment in people with OPD [118]. MBSImP measures 17 components of swallowing impairment in oral, pharyngeal, and esophageal regions through analysis of VF data using ordinal severity scales of 17 components: six oral, ten pharyngeal, and one esophageal. Each component is rated based on specific criteria that were established and validated through expert consensus and repeated testing. Establishing HRCA signal features that predict MBSImP ratings can demonstrate the value of HRCA in the screening and diagnostic processes and potentially obviating the need for VF in some cases. Furthermore, combining MBSImP and PAS [81, 109, 119] leads to a complete multidimensional profile of swallow impairment and potential dysphagia-related risk to which HRCA can be equated. MBSImP has been used concurrently in several studies with PAS and both measures have shown their complementary value in the comprehensive quantification of swallow impairment and the airway protection outcomes that these impairments produce [118, 120-124].

**A2.c. Justification and feasibility – Preliminary studies:** Our pilot study has identified strong differences in clusters of HRCA signal features that clearly separated less- and more-severely impaired swallows. We analyzed 100 swallows from our 274-patient data set, to determine if HRCA signal features can detect swallow kinematic events. All 100 swallows were simultaneously observed with VF and HRCA sensors, and 13 swallow

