**Table 2 –** Frequency of signal maxima co-occurring with swallow kinematic events; separated by PAS ranges PAS 1-2 vs. PAS 3-8. NUME denotes the number of signal maxima co-occurred with swallow kinematic events > 50% of the time. MIC denotes a microphone, while S-I, A-P, and M-L denote vibrations in superior-inferior, anterior-posterior, and medial-lateral directions captured by an accelerometer.

Sensor	NUME	PAS 1-2		PAS 3-8	
		overall %	range	overall %	range
MIC	80/91	49	37-65	13.6	10-18
S-I	64/91	45	29-62	11	7-16
A-P	55/91	43	26-62	11	6-17
M-L	48/91	40	25-61	10	3-16

**A2.d. Experimental approach:** STEP 1: All swallows from patients and healthy participants (Aim 1) will be rated using the MBSImP. Judges will undergo standardized training in visual inspection and MBSimP ratings of swallow kinematic functions and impairments, and establishment of inter- and intra-rater reliability before beginning scoring. STEP 2: In addition to MBSimP component 16 (pharyngeal residue), pharyngeal residue (valleculae, pyriform sinuses) will be measured using the Normalized Residue Rating Scale which standardizes areas of barium residue retained in pharyngeal recesses (valleculae, pyriform sinuses) using conversion factors based on individual patient height [112]. STEP 3: We will measure airway compromise using the PAS [109]. STEP 4: Pre-process HRCA recordings per steps taken in previous publications [29, 30, 71] to remove any disturbances and diminish noise in these recordings.

STEP 5: We will develop an algorithm based on the state-of-the-art machine learning concepts whose output will be the differentiation between healthy controls and people with suspected dysphagia whose swallows did not exhibit dysphagia, healthy dysphagic (see Figure 11). Specifically, we will utilize a random 70% training subsample for the deep belief machine learning approach as in our preliminary works [70], and once modeling is complete, use the remaining 30% validation subsample to obtain accuracy estimates devoid of model overfitting.

**A2.e. Data interpretation:** We will employ the same deep learning methods as in Aim 1 for our primary analysis, but instead will employ techniques suitable for categorical, ordinal dependent variables such as MBSimP and PAS. In addition, we will employ regression tree and linear mixed model methods in an effort to obtain simpler

**Figure 11 –** Our proposed experimental and data analysis approach for Aim 2.

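### Aims 1 and 2 each state a random 70/30 split of the same, partly reused data without locking one split or excluding earlier-used patients, so the hold-out is internal validation

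*Combined protocol and SAP*

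**What the plan says.** A1.d STEP 4 pools the swallows of the new healthy participants with more than 4000 patient swallows from the previous grant. In STEP 5 "we will analyze a random 70% training subsample and use the deep belief machine learning approach as in our preliminary work [70", and then "the remaining 30% validation subsample will be used to obtain accuracy estimates devoid of model overfitting". A1.e describes the confusion matrix and cross-validation for the training part, brings in the hold-out last, and states: "we will use the validation subsample to obtain authoritative measures of accuracy devoid of risks of model overfitting".

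A2.d STEP 1 takes the same patients and healthy participants. In STEP 5 "we will utilize a random 70% training subsample for the deep belief machine learning approach as in our preliminary works [70", with the other 30% again used for validation and again described as free of overfitting. It does not refer back to the Aim 1 split. Neither section limits who may be held out.

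On earlier use of the data:

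- The Significance section says that the existing methods come from work on the 274 patients with suspected OPD alone.
- A2.c: "We analyzed 100 swallows from our 274-patient data set". A1.e counts 3900 others besides these, so the 100 stay in the pool of 4000.
- A1.c reports the deep belief network work [70] on 55 healthy people and a patient group: "The non-healthy participants consisted of a total of 53 patients (34 men, 19 women, mean age 63) with suspected dysphagia". Figure 9 lists 18 configurations and bolds the best.
- The progress report presents [70] as project output: "Figure 7 summarizes the main results of [70". It also places [70] in the project's publication range, [65-77].

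**The concern.** A hold-out earns the word authoritative only if the people in it played no part in shaping the method, and if later modelling does not start from knowledge gained on them. Here the pool is mostly an existing database that has already served method development. A plain random draw can put those patients into validation. A second draw for Aim 2 can put Aim 1 training patients into Aim 2 validation.

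What is at stake is how far a reader may trust the accuracy figures for Aims 1 and 2, which supply the algorithm for Aim 3. A1.f sets a benchmark of over 90% accuracy with reference to [70], and in Figure 9 only one of the 18 configurations exceeds 90%. A1.b also criticises earlier studies for not separating training from testing groups clearly, so the plan should meet that standard itself.

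**Working it through.** **Inputs.** From A1.h: 4000 swallows from 274 patients; 650 swallows expected from 65 healthy people; sensitivity and specificity 90%; design effect 3.8; 95% confidence. From A1.c: 53 patients. From Figure 9: the 18 configurations.

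**1. The plan's own margins for sensitivity.** Margin = 1.96 × √(0.9 × 0.1 / n_eff), with n_eff = swallows / 3.8.

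- Training: 0.7 × 4000 = 2800; 2800/3.8 = 737; ±2.2% (stated ±2%).
- Validation: 0.3 × 4000 = 1200; 1200/3.8 = 316; ±3.3% (stated ±3%).

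These reproduce. The specificity margins do not follow from the same inputs (±5.4% and ±8.2%, against ±8% and ±13% stated). The stated values are the more cautious, and they concern the healthy side, where there is no reuse.

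**2. Possible overlap with [70].** The documents do not say how many of the 53 are among the 274, so the range is 0 to 53.

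- Maximum share: 53/274 = 19.3%.
- Expected number in the hold-out at that maximum: 0.30 × 53 = 15.9, of 0.30 × 274 = 82 patients.
- Healthy side: none. The 70 are newly recruited and are not the earlier 55.

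**3. Rough bound on optimism from choosing the network.** Treat the whole gap between the bolded configuration and the average of the 18 as optimism, and apply it to the maximum overlap.

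- Sensitivity: 85.7 − 80.7 = 5.0; 5.0 × 0.193 = 1.0 point.
- Accuracy: 91.3 − 87.2 (mean) = 4.1; 4.1 × 0.193 = 0.8 points. Against the median of 87.45: 3.85 × 0.193 = 0.7 points.

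All lie inside the ±3% validation margin.

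**4. The A2.c pilot.** 100/4000 = 2.5% of swallows, from at most 100 patients.

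**5. If Aim 2 is drawn again independently.** There are 4000 + 650 = 4650 swallows, and 0.3 × 4650 = 1395 in each hold-out.

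- Aim 2 validation units already in Aim 1 training: 70%, about 977 swallows.
- Units held out in both aims: 0.3 × 0.3 = 9%, about 419 swallows.
- With one shared split, no hold-out unit is in either training set.

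**6. Is there room to exclude earlier-used patients?**

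- Without the 53: 274 − 53 = 221 patients.
- If the pilot came from 100 further patients: 221 − 100 = 121. Both exceed the 82 needed.
- If the hold-out is instead 30% of the 221: 4000 × 221/274 = 3226 swallows; 0.3 × 3226 = 968; 968/3.8 = 255; margin ±3.7% instead of ±3.3%.

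**The case against.** The strongest reply has five parts.

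- **Membership of the 53 is inferred.** A1.c never places them in the database, whereas A2.c names the database when it uses it. The document also cites [70] for two different analyses: the feature table in Figure 7 and the deep belief classifier. The publication list, as available here, has an entry that fits the first but no deep belief classifier of swallows. This stands. A reader might infer that the network was picked on the validation patients; the documents make that plausible but do not establish it.
- **Only a model family is carried over.** A1.d fixes none of the 18 configurations, the model is refitted on training data, and the hold-out comes last. This stands, and it is why the step from a median of 87.45% to 91.3% must not be read as the bias.
- **A second draw is one reading.** A2.d does not say new, and it does not say shared. This stands, but either reading needs a sentence in the plan.
- **Swallows that trained one model do not leak into a separately fitted one.** A2.a, A2.e and A2.f describe ordinal impairment scores judged by root mean square error and R². This stands in part: A2.d STEP 5 repeats the Aim 1 classification target and approach, so tuning can carry over. A reader might also infer that a redraw spoils Aim 1. It cannot, because it comes after that estimate.
- **Aim 3 tests new patients.** It does, but with about 46 after refusals and with logistic models fitted on those same patients, so it is a limited check.

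**Conclusion.** The plan neither ties the two splits together nor keeps earlier-used patients out of validation, and its description of the hold-out is too strong. What it provides is internal validation.

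The consequence is modest. Optimism from network selection is roughly 1 point of sensitivity at most, on the patient side only, and zero if none of the 53 are in the database. That bound assumes full overlap and counts the whole gap in Figure 9 as optimism. It covers neither feature choices influenced by the A2.c pilot nor other earlier analyses of the database, which the documents do not allow one to quantify.

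The Aim 2 part rests on the assumption of an independent redraw. In that case 70% of Aim 2 validation units would come from Aim 1 training. These are shares of reused data, not a measured bias, and the route is carried-over tuning. The margins take the plan's design effect of 3.8 as given. This is a cheap improvement worth making, not a flaw that invalidates either aim.

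**What to change.** Replace the split sentences in A1.d STEP 5 and A2.d STEP 5 with one rule, for example: *Before any modelling, participants will be divided once, by person, into training and validation sets. The list of IDs will be locked and used in both Aims 1 and 2. Patients whose recordings were used in [70], if they are in the database, or in the A2.c pilot will be assigned to training; the validation set will be drawn at random from the remainder.* The sponsor can settle the overlap by matching patient IDs. The shared hold-out should be scored only after each aim's model is fixed, so that the Aim 1 result does not steer Aim 2.

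If earlier use proves too wide to leave an adequate hold-out, keep the single locked split and reword A1.e and A2.d to call the result internal validation.

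**Cost.** An ID check, a rule in the split program and a few sentences. The hold-out is then no longer a simple random sample of all patients, which should be stated. If it stays at 82 patients, the sensitivity margin remains about ±3.3%; at 30% of the remaining 221 it widens to about ±3.7%. The plan does not state whether the split is by person or by swallow. That is a separate gap, but this rule works only if each person's swallows stay together.

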
**A1.f. Expected outcomes:** The benchmark for success of Aim 1 will be creation of a machine learning algorithm that completes the continuum of of HRCA signal characteristics from normal to the most severely impaired swallowing function that will then be available for future research. Specifically, we anticipate these algorithms

will correctly identify normal airway protection (PAS scores of 1-2) in healthy controls and patients with dysphagia with over 90% accuracy compared to the gold standard VF ratings for each swallow [70]. These outcomes will establish the evidence that the HRCA signals and advanced analytics form a robust and reliable swallowing screening system with comparable accuracy to VF, while also demonstrating the system's ability to identify additional swallowing diagnostic features that are currently only possible with VF, potentially advancing HRCA as not a screening tool with diagnostic capabilities far beyond SIS.

**A1.g. Challenges and contingency plans:** The preliminary results (see A1.c.) strongly support our hypothesis (see A1.a.). In the highly unlikely event that our VF judges' ratings drift unacceptably, we will increase surveillance on inter- and intra-rater reliability and pull judges from analysis and retrain them to criterion, retest their reliability before placing them back online.

**A1.h. Sample size justification:** We currently have data on 4000 swallows from 274 dysphagic persons. We plan to add 700 swallows from 70 healthy persons to this data set. Allowing for some refusals, we anticipate obtaining 650 swallows from 65 healthy persons. Assuming the sensitivity and specificity will be approximately 90%, intra-class correlation of 0.7 from our prior data and a resulting design effect of 3.8 [114], and using published methods [115, 116] implemented in commercially available software (PASS 2012, Number Cruncher Statistical Systems, Kaysville, UT), conservatively we will be able to estimate sensitivity with a margin of error as small as  $\pm 2\%$  and specificity with  $\pm 8\%$  in the training sample, and  $\pm 3\%$  and  $\pm 13\%$  in the validation samples, at the 95% confidence level.

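### A1.h: the design effect of 3.8 does not match the section's own swallow counts, and at ICC 0.7 the ±2% training margin for sensitivity cannot be reached with persons as clusters

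*Combined protocol and SAP*

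**What the plan says.** Section A1.h (sample size justification for Aim 1) starts from the existing data, "We currently have data on 4000 swallows from 274 dysphagic persons", and adds healthy volunteers: "we anticipate obtaining 650 swallows from 65 healthy persons". It assumes sensitivity and specificity near 90% and an "intra-class correlation of 0.7 from our prior data and a resulting design effect of 3.8". From these it claims "conservatively we will be able to estimate sensitivity with a margin of error as small as" ±2% in the training sample and ±3% in the validation sample. For specificity it gives ±8% and ±13%. All are at 95% confidence. It does not name the cluster or the number of swallows per cluster.

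Other sections bear on these figures:

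- A1.d STEP 1 has each healthy subject make ten swallows, five at each of two bolus volumes.
- A1.d STEP 5 says "we will analyze a random 70% training subsample", with the other 30% kept for validation. It does not say whether persons or swallows are drawn. A2.d STEP 5 uses the same split.
- A1.e adds leave-one-out and 10-fold cross-validation, again without a unit, and treats the validation subsample as the decisive measure of accuracy.
- The target of the classifier varies. A1.d STEP 5 wants to "differentiate between healthy controls and people with suspected OPD whose swallows did not exhibit OPD". A1.e says "The confusion matrix will be calculated by comparing the algorithm's output with scores from STEP 2", that is, the videofluoroscopy ratings. A1.f expects that the algorithms "will correctly identify normal airway protection (PAS scores of 1-2) in healthy controls and patients with dysphagia".
- A2.h carries over the ICC of 0.7 and the design effect of 3.8, and derives detectable R-squared values of 0.03 (training) and 0.06 (validation).

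**The concern.** A design effect follows from the ICC and the cluster size. Here the ICC and the result are given, so the cluster size can be solved for, and it does not match the counts two sentences earlier. At an ICC as high as 0.7, further swallows from the same person add little information, so a design effect that is too small makes the precision look better than it is.

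The training margin is presented as conservative. The validation margin matters more, because A1.e relies on that subsample for its accuracy claim. Whether ±3% is realistic there depends on a choice the plan leaves open. If swallows are drawn, the algorithm is tested on people it was trained on, which weakens the protection against overfitting that the 30% subsample is meant to give. Aim 3 takes its algorithm from Aims 1 and 2.

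**Working it through.** **Inputs.** From A1.h: 4000 swallows from 274 patients, 650 from 65 healthy persons, ICC 0.7, design effect 3.8, sensitivity and specificity 0.90, 95% confidence. From A1.d: 70/30 split and 10 swallows per healthy subject. Assumption: sensitivity is estimated on patient swallows, unless stated otherwise.

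**Formulas.** DEFF = 1 + (m − 1) × ICC. Effective n = swallows / DEFF. Margin = 1.96 × √(0.9 × 0.1 / effective n). Exact (Clopper–Pearson) half-widths are given where they matter.

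**1. Reproducing the stated sensitivity margins with 3.8**

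- Training: 2800 / 3.8 = 737, margin ±2.2%, printed as ±2%.
- Validation: 1200 / 3.8 = 316, margin ±3.3%, printed as ±3%.

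**2. What 3.8 implies**

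- 3.8 = 1 + (m − 1) × 0.7 gives m = 5 exactly.
- Patients: 4000 / 274 = 14.6, so DEFF = 1 + 13.6 × 0.7 = 10.5.
- Healthy persons: 650 / 65 = 10, so DEFF = 1 + 9 × 0.7 = 7.3.
- To keep 3.8 at 14.6 swallows per patient, the ICC would have to be 2.8 / 13.6 = 0.21.

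**3. Whether ±2% can be reached.** With K persons and any number of swallows each, effective n cannot exceed K / ICC.

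| Basis | Effective n | Margin |
|---|---|---|
| 274 patients, ceiling 274 / 0.7 | 391 | ±3.0% |
| 339 persons pooled, ceiling 339 / 0.7 | 484 | ±2.7% |
| Needed for ±2.0%: 0.09 × (1.96 / 0.02)² | 864 | – |
| Needed for ±2.5%, the edge of rounding to ±2% | 553 | – |

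Both ceilings fall short of 553.

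**4. Margins on the plan's counts, all 274 patients contributing**

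| Split | Training | Validation |
|---|---|---|
| By person, DEFF 10.5 | 2800 / 10.52 = 266, ±3.6% (exact ±3.8%) | 1200 / 10.52 = 114, ±5.5% (exact ±5.9%) |
| By swallow | m = 10.2, DEFF 7.45, n = 376, ±3.0% | m = 4.4, DEFF 3.37, n = 357, ±3.1% |
| By person, 5 swallows per patient, DEFF 3.8 | 1370 × 0.7 / 3.8 = 252, ±3.7% | 1370 × 0.3 / 3.8 = 108, ±5.7% |

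If only half the patients contributed to the denominator (an assumption, for scale), the person split would give 133 and 57 effective observations, or ±5.1% and ±7.8%.

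**5. Specificity (exact half-widths)**

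- 3.8 on 455 / 195 healthy swallows: ±5.8% / ±9.1%. This does not match the plan.
- 7.3 on 455 / 195: ±8.2% / ±13.0%. This matches.
- 3.8 on five swallows per healthy person (65 × 5 = 325, split 227.5 / 97.5): ±8.4% / ±13.3%. This also matches.

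**6. A2.h.** With 4700 swallows and 3.8, effective n is 866 / 371. With 20 predictors, 80% power and α = 0.05 (noncentral F), the detectable R-squared is 0.024 / 0.056. The stated 0.03 / 0.06 are these values rounded up, so they rest on 3.8.

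**The case against.** The strongest defence is that A1.h never says the cluster is the person. A1.d has five swallows at each of two bolus volumes and sorts data by volume. Clusters of five swallows per person and bolus condition would give 3.8 at ICC 0.7, and on five swallows per healthy person they fit the stated specificity margins. This stands as a possible origin of 3.8, though it is an inference. A reader might conclude that no reading reconciles the figures; that goes too far. But the reading does not rescue sensitivity. Five swallows from each of 274 patients give ±3.7%. Using all 4000 swallows as 800 clusters of five requires swallows by the same person under different conditions to be independent.

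A1.h also assumes only approximately 90% sensitivity and hedges its margins. At 94%, the swallow-split training n of 376 gives 1.96 × √(0.94 × 0.06 / 376) = ±2.4%, which rounds to ±2%. This is fair, but 90% is the value the plan uses.

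The training margin decides nothing by itself, and the plan's silence on the split does not show that swallows will be drawn. The printed margins do not reveal it either, since 70% of patients and 70% of swallows both give about 2800 swallows. The point is therefore a request to state the unit.

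On Aim 2, A2.h itself regards classical sample size methods as ill-suited, and A2.e plans linear mixed models alongside deep learning. Predictors that vary from swallow to swallow may need less inflation than an outcome proportion.

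**Conclusion.** The point holds for sensitivity. A1.h's design effect does not fit its own counts, and the ±2% training margin is better than the data can give with persons as clusters, ICC 0.7 and 90% sensitivity. The ceiling of ±3.0% applies to a patients-only denominator; with healthy persons pooled it is ±2.7%. On a person-level split with all 274 patients, the margins are about ±3.6% and ±5.5% (exact ±3.8% and ±5.9%), against the stated ±2% and ±3%. The validation ±3% is nearly met on a swallow-level split, but then the validation is not independent of the training persons. A lower ICC would narrow all of these, but 0.7 is the value the plan attributes to its prior data.

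Three stronger conclusions are tempting but unsupported:

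- That the specificity margins are wrong: two bases reproduce them, and the plan does not say which was used.
- That R-squared of 0.03 / 0.06 cannot be detected: the values lose their derivation, but no ICC is given for the predictors, so they are not shown to be unattainable.
- That the randomized comparison is compromised: the Aim 3 calculation in A3.h does not use 3.8.

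**What to change.** - **A1.h.** Name the cluster, the swallows per cluster, the source of the ICC, and the persons and swallows in each denominator. Recompute the design effect: 10.5 if all 4000 swallows of 274 patients count at ICC 0.7, or state a lower ICC if the prior data support one. At ICC 0.7, restate the sensitivity margins as no better than about ±4% (training) and ±6% (validation) when all 274 patients contribute. State the basis of the specificity margins.
- **A1.d and A2.d STEP 5, and cross-validation in A1.e.** Say that all swallows of one person go to the same subsample and the same fold.
- **A1.e.** Compute accuracy intervals with person-level clustering, for example a bootstrap over persons.
- **A2.h.** Recompute the detectable R-squared with the corrected design effect, or justify a smaller inflation. No replacement value is proposed here.

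The cost is a few sentences, restated figures and clustered intervals, with no added participants. The downside is that the stated precision becomes less favourable.
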